# 5 Study Design

This is a double-blinded sham control clinical trial seeking to determine the safety and efficacy of the Solius Photobiologic System in increasing the serum concentrations of 25(OH)D in a vitamin D deficient/insufficient adult population. We will make our best effort to recruit individuals with all Fitzpatrick skin types as requested by the FDA. The study will be conducted at Boston University after it is approved by Boston University's Institutional Review Board.

	Table 1: Fitzpatrick Skin Types												
Skin type	Typical Features	Tanning ability											
ł	Pale white skin, blue/green eyes, blond/red hair	Always burns, does not tan											
11	Fair skin, blue eyes	Burns easily, tans poorly											
111	Darker white skin	Tans after initial burn											
IV	Light brown skin	Burns minimally, tans easily											
V	Brown skin	Rarely burns, tans darkly easily											
VI	Dark brown or black skin	Never burns, always tans darkly											

Each subject will be categorized into one of 6 Fitzpatrick skin types, type I, II III, IV and skin type V or VI. Skin types V and VI will be combined to represent the group with the darkest skin tone for subgroup analysis.

A total of 80 adult subjects with 5 skin types groups (I, II, III, IV and V/VI) will be enrolled for vitamin D deficiency/ insufficiency screening. The screening test for 25(OH)D will be performed by the Boston Medical Center's clinical laboratory for local Quest diagnostic laboratory which is able to perform the test within 24 hours. We expect at least 80% of the population in the Boston area has a level of 25(OH)D

below 30 ng/ml. Thus, we expect to enroll approximately 100 subjects with different group skin types to enroll 80 vitamin D deficient or insufficient subjects in this study. The research coordinator will be responsible for randomization and allocation. Thus, the study will be blinded to other members of the research team. Solius and the PI will have no contact with the participants. Subjects will be selected to or not to receive the UVB intervention (40 subjects in the treatment group and 40 subjects in the control group) (Figure 1). Two study groups will be matched by age, sex, BMI, and skin type by stratified randomization.

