# 12 Statistical Plan

The endpoint is the difference in vitamin D insufficiency/sufficiency prevalence between the treatment and the control group use at 16 weeks of follow-up. The subject will have at least one serum 25(OH)D

evaluation within 16 weeks, and at least one phototherapy session in the 16 weeks follow up. The protocol includes a sample size calculation, which allowed for a loss to follow-up of 15%.

Statistical analysis will be performed using SPSS Statistics, version 25 (IBM Corporation). Age, sex, BMI, and Fitzpatrick skin type will be matched in two study groups. Two-sided P < .05 will be considered significant. All models will be developed according to the intention-to-treat principle. A supportive analysis will also be conducted on the per-protocol (PP) population.

The biological and clinical characteristics at enrolment will be presented, and all variables for the participants in the treatment and control groups will be compared at each follow-up using Fisher's exact test for categorical variables and a Mann–Whitney *U* test for continuous variables. For intergroup differences, 95% CIs will be also calculated. The endpoint, the proportion of subjects converting from vitamin D deficiency/insufficiency to vitamin D insufficiency/sufficiency at 16 weeks will be compared between groups using Fisher's exact test and logistic regression adjusting for skin types. Secondary analysis will be involved a comparison of changing in serum levels of 25(OH)D between groups using a Mann–Whitney *U* test and linear regression adjusting for skin types. A linear mixed model will be used to examine the relationship between phototherapy and serum 25(OH)D3 at different time points, adjusting for the baseline values and correlation of outcomes within individuals and season.

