## 12.2 Sample Size Determination

The endpoint of this study is to compare the improvement of vitamin D status between treatment group and the controls. A previous study by Chandra et al. demonstrated the increase in the mean serum 25(OH)D in subjects with malabsorption syndrome receiving UV therapy from 21± 3 ng/mL to 27±4 ng/mL after 8 weeks (13). We would expect that to increase the serum 25(OH)D level by 10 ng/mL (SD=5ng/ml), after 16 weeks based on a previous study (13) as well as an earlier pilot study that was completed by Solius.

The endpoint is to improve vitamin D status in the treatment group compared to sham controls. We expect that the serum levels of 25(OH)D will increase more than 10 ng/ml (SD=5ng/ml) after 16 weeks of intervention in the treatment group compared to controls. Subjects converted from vitamin D deficient/insufficient to insufficient/sufficient is considered a minimum clinical important difference (MCID). We expect at least 70% of vitamin D deficient/insufficient subjects in the treatment group to convert to insufficient/ sufficient. Also, because of seasonal variations and other confounders, we expect maximum 30% of subject convert to insufficient/sufficient in sham control. With the desired power of 80% and significance level ( $\alpha$ ) of 0.01, the sample size in each group is 35.

Approximately 100 adult subjects with 5 skin types group (I, II, III, IV and V/VI) will be enrolled for vitamin D deficiency/ insufficiency screening. We expect that at least 80% of the population in the

Boston area has a level of 25(OH)D below 30 ng/ml. Thus, we will enroll 100 subjects with different skin types to enroll 80 vitamin D deficient or insufficient subjects in this study. We plan to match treatment and control group for age, sex, BMI and skin type by stratified random sampling (40 subjects in each group). In our experience, the rate of screen failure and subject dropout is 10-15%. Then, we expect to have at least 35 subjects per each group.

Parameters	Value
Conversion of the subjects from vitamin D deficient to vitamin D	70%
insufficient/sufficient or vitamin D insufficient to vitamin D sufficient in the	
treatment group after 16 weeks (P1)	
Conversion of the subjects from vitamin D deficient to vitamin D	30%
insufficient/sufficient or vitamin D insufficient to vitamin D sufficient in the control	
group after 16 weeks (P2)	
Significant level	0.01
Power	80%

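### Randomisation is stratified on age, sex, BMI and skin type, but the regressions adjust for skin type alone and the mixed model for none of the four; aligning them is a cheap gain in precision, of a size the documents do not fix.

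*Combined protocol and SAP*

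**What the plan says.** Section 5 describes the allocation: "Two study groups will be matched by age, sex, BMI, and skin type by stratified randomization". Section 12.2 repeats it: "We plan to match treatment and control group for age, sex, BMI and skin type by stratified random sampling", with 40 subjects per group. Section 12 says again that the groups will be matched on these four factors. Nowhere are cut-points given for age or BMI, and no reason is given for choosing these four.

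Section 12 then sets out the analyses:

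- Conversion at 16 weeks is compared with a Fisher test and "logistic regression adjusting for skin types".
- The change in 25(OH)D is compared with a Mann–Whitney test and "linear regression adjusting for skin types".
- A linear mixed model for 25(OH)D over time is fitted "adjusting for the baseline values and correlation of outcomes within individuals and season". None of the four stratification factors is in that list.

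Other sections give skin type particular weight. Section 12.1 expects types I and II to respond most. Section 8 makes the titration dose range depend on skin type, Section 9 does the same for session length, and Section 5 plans skin-type subgroups.

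**The concern.** Stratifying on a factor takes its variation out of the treatment contrast. If the model then omits the factor and the factor predicts the outcome, that variation stays in the residual. The reported standard error then exceeds the true spread of the estimate, the confidence interval is wider than the design earned, and the test rejects less often than its nominal level. This is a loss of precision. It is not bias, and it does not raise the false-positive rate.

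The clearest case is the mixed model. It uses the repeated blood draws, yet it leaves out the one factor that the plan itself ties to response, dose and exposure time.

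**Working it through.** **Plan's own figure.** Section 12.2 uses 70% v 30% conversion, two-sided alpha 0.01 and 80% power. With its rounded z values: {2.58 × √(0.5 × 0.5 × 2) + 0.84 × √(0.21 + 0.21)}² / 0.4² = (1.824 + 0.544)² / 0.16 = 35.07, which reproduces the stated 35 per group. Nothing below changes that figure.

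**Linear and mixed models, near-perfect balance.** Let R² be the share of the variance left by the covariates already in the model that the omitted factors explain. The documents give no value, so a range is assumed. Reported SE / true SE = 1/√(1 − R²). The true size of a nominal 5% test is 2{1 − Φ(1.96/√(1 − R²))}. Where the correctly adjusted test has 80% power, the unadjusted one has Φ(1.960 + 0.842 − 1.96/√(1 − R²)).

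For R² = 10%: 1/√0.90 = 1.054; 1.96 × 1.054 = 2.066; size = 3.9%; power = Φ(0.736) = 76.9%.

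| R² (assumed) | SE ratio | True size | Power (adjusted test 80%) |
|---|---|---|---|
| 0 | 1.000 | 5.0% | 80.0% |
| 5% | 1.026 | 4.4% | 78.5% |
| 10% | 1.054 | 3.9% | 76.9% |
| 20% | 1.118 | 2.8% | 72.9% |
| 30% | 1.195 | 1.9% | 67.7% |

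For the mixed model these figures are an approximation to the contrast at a single visit. Baseline and season are already in that model, so R² refers to what remains after them.

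**Sparse strata.** With five skin groups ("Approximately 100 adult subjects with 5 skin types group (I, II, III, IV and V/VI") and age and BMI each cut in two (assumed), there are 5 × 2 × 2 × 2 = 40 strata, and 80/40 = 2 subjects per stratum. Balance will then be imperfect. A simulation with ordinary blocks of four within strata plus dropout gave an SE overstatement of about 2% (R² = 10%) or 4% (20%), with true size 4.6% or 4.1%.

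**Linear model at the planned effect.** With SD 5 and 35 per group, the SE of the difference is 5 × √(2/35) = 1.195 ng/mL. The planned 10 ng/mL is 8.4 such SEs, so power is about 100% with or without adjustment. At 2.5 ng/mL (the minimum four-week gain in Section 12.2, read as a between-group difference and with SD 5 assumed at that visit too), 2.5/1.195 = 2.092. Without adjustment, power is Φ((2.092 − 1.960)/√(1 − R²)); with it, Φ(2.092/√(1 − R²) − 1.960). That is 56% v 60% for R² = 10%, and 56% v 65% for 20%.

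**Logistic model.** Simulation: 80 subjects balanced over the 40 strata, 12.5% dropout, 70% v 30% conversion, 1,500 replicates. The joint strength of age, sex and BMI is assumed, as an SD on the log-odds scale. Both alphas are shown because Section 12.2 sizes the trial at 0.01 and Section 12 tests at 0.05.

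| Log-odds SD | Power at 0.05: skin type only → all four | Power at 0.01: skin type only → all four |
|---|---|---|
| 0 | 94.9 → 95.1% | 81.0 → 82.2% |
| 0.5 | 95.3 → 96.0% | 83.5 → 85.9% |
| 1.0 | 95.3 → 97.1% | 82.5 → 88.5% |
| 1.5 | 96.0 → 98.7% | 84.7 → 92.7% |

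The gain does not come from a smaller SE. At log-odds SD 1.0, adjustment raises the median SE of the log-odds ratio from 0.572 to 0.723 and moves the median estimate from 1.901 to 2.485, so their ratio goes from 3.32 to 3.44. Under no effect, the size of the skin-type-only Wald test at nominal 5% was 5.9%, 5.0%, 3.5% and 2.1% across the four rows. It is conservative only when the omitted factors are strong.

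**The case against.** The best case for leaving the plan alone is that nothing it promises is at risk. At the planned effect the linear model has essentially full power, and the logistic model at 0.05 is already near 95%. The documents do not say how strongly any factor predicts 25(OH)D. Balance over some 40 small strata would be imperfect, which reduces the overstatement. Adding terms also has a price in a logistic model with few events: treatment, four skin-type terms, sex, age and BMI make eight terms besides the intercept for about 35 converters (35 × 0.7 + 35 × 0.3). All of this stands, and it limits the size of the point. It does not justify the omission. Where balance fails, adjustment corrects chance imbalance; where it holds, adjustment recovers precision.

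A reader might infer more than the documents support:

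- *That the standard errors are certainly too wide.* This needs prognostic strength that is nowhere stated. Section 12.1 links only skin type to outcome, and there as response to phototherapy, which is not a share of variance in both arms.
- *That the same mechanism applies to the logistic regression.* It does not: adjustment raises the SE of the log-odds ratio.
- *That the trial is underpowered as a result.* The plan's 10 ng/mL with SD 5 is a 2 SD effect. A material loss in the linear model appears only at much smaller effects.
- *That the four factors were chosen because they are believed to drive 25(OH)D.* No reason for the choice is given.
- *That the linear and mixed models give the same effect under two adjustment sets.* One concerns change and the other levels at several visits, so they need not agree.

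**Conclusion.** The mismatch between design and analysis is plain in the text: four stratification factors, one of them in the regressions, none in the mixed model, and none in the Fisher or Mann–Whitney tests. Its consequence is conditional. For the linear and mixed models, standard errors can be about 5% or 12% too wide if the omitted factors explain 10% or 20% of the remaining variance under near-perfect balance. The figure is roughly 2% or 4% with sparse strata, and nil if the factors are not prognostic. For the logistic model the available gain is about 0 to 3 points of power at 0.05 and 1 to 8 at 0.01. These sizes rest on assumed prognostic strength and assumed two-level cuts of age and BMI. This is a cheap improvement and not a flaw that threatens the conclusion. The case is strongest for skin type in the mixed model, then for the linear regression, and weakest for the logistic regression.

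**What to change.** In Section 12:

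- Mixed model: add skin type (five groups), sex, and age and BMI as continuous covariates.
- Linear and logistic regressions: add sex and continuous age and BMI to skin type.
- Conversion endpoint: report the adjusted result as a standardised difference in proportions with a 95% CI beside the odds ratio, since Section 12 states the endpoint as a difference.
- Say whether the conclusion rests on the adjusted models or on the Fisher and Mann–Whitney tests, which cannot use the factors.

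The cost is SAP wording and modest programming; allocation already requires all four variables. The mixed model gains seven parameters (four for skin type, three for sex, age and BMI) and each regression gains three. If the factors prove non-prognostic, the linear-model SE grows by about 1%. In small samples the logistic likelihood-ratio test drifts a little further above nominal: 6.4% to 7.2% at a nominal 5% in a separate simulation. If only part of this is adopted, change the mixed and linear models first.

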## 12.1 Study Hypotheses

We suspect that with the incorporation of a 16-week phototherapy regiment, at least 70% of vitamin D deficient/insufficient subjects in the treatment group will convert to insufficient/ sufficient. Also, because of seasonal variations and other confounders, we expect a maximum 30% of the subjects to convert to insufficient/sufficient in sham control. In particular, we expect individuals with Fitzpatrick Type I and II skin to show the greatest response to phototherapy.

## 12.2 Sample Size Determination

The endpoint of this study is to compare the improvement of vitamin D status between treatment group and the controls. A previous study by Chandra et al. demonstrated the increase in the mean serum 25(OH)D in subjects with malabsorption syndrome receiving UV therapy from 21± 3 ng/mL to 27±4 ng/mL after 8 weeks (13). We would expect that to increase the serum 25(OH)D level by 10 ng/mL (SD=5ng/ml), after 16 weeks based on a previous study (13) as well as an earlier pilot study that was completed by Solius.

The endpoint is to improve vitamin D status in the treatment group compared to sham controls. We expect that the serum levels of 25(OH)D will increase more than 10 ng/ml (SD=5ng/ml) after 16 weeks of intervention in the treatment group compared to controls. Subjects converted from vitamin D deficient/insufficient to insufficient/sufficient is considered a minimum clinical important difference (MCID). We expect at least 70% of vitamin D deficient/insufficient subjects in the treatment group to convert to insufficient/ sufficient. Also, because of seasonal variations and other confounders, we expect maximum 30% of subject convert to insufficient/sufficient in sham control. With the desired power of 80% and significance level ( $\alpha$ ) of 0.01, the sample size in each group is 35.

Approximately 100 adult subjects with 5 skin types group (I, II, III, IV and V/VI) will be enrolled for vitamin D deficiency/ insufficiency screening. We expect that at least 80% of the population in the

Boston area has a level of 25(OH)D below 30 ng/ml. Thus, we will enroll 100 subjects with different skin types to enroll 80 vitamin D deficient or insufficient subjects in this study. We plan to match treatment and control group for age, sex, BMI and skin type by stratified random sampling (40 subjects in each group). In our experience, the rate of screen failure and subject dropout is 10-15%. Then, we expect to have at least 35 subjects per each group.

Parameters	Value
Conversion of the subjects from vitamin D deficient to vitamin D	70%
insufficient/sufficient or vitamin D insufficient to vitamin D sufficient in the	
treatment group after 16 weeks (P1)	
Conversion of the subjects from vitamin D deficient to vitamin D	30%
insufficient/sufficient or vitamin D insufficient to vitamin D sufficient in the control	
group after 16 weeks (P2)	
Significant level	0.01
Power	80%

$$\begin{split} N_1 &= \left\{ z_{1-\alpha/2} * \sqrt{\bar{p} * \bar{q} * (1 + \frac{1}{k})} + z_{1-\beta} * \sqrt{p_1 * q_1} + (\frac{p_2 * q_2}{k}) \right\}^2 / \Delta^2 \\ q_1 &= 1 - p_1 \\ q_2 &= 1 - p_2 \\ \bar{p} &= \frac{p_1 + k p_2}{1 + K} \\ \bar{q} &= 1 - \bar{p} \\ N_1 &= \left\{ 2.58 * \sqrt{0.5 * 0.5 * (1 + \frac{1}{1})} + 0.84 * \sqrt{0.7 * 0.3 + (\frac{0.3 * 0.7}{1})} \right\}^2 / 0.4^2 \\ N_1 &= 35 \\ N_2 &= K * N_1 = 35 \\ N_2 &= K * N_1 = 35 \\ \end{split}$$

The research coordinator will be responsible for randomization and allocation. Thus, the study will be blinded to other members of the research team. We expect that the serum levels of 25(OH)D will increase by at least 10 ng/ml in the treatment group compared to the control group after 16 weeks UV exposure in a linear fashion. We will do an assessment every four weeks, expecting that there will be a minimum of 2.5 ng/ml increase in the serum 25(OH)D. We will conduct the blinded interim analyses to re-assess the planned sample size after thirty five subjects in each group have completed four weeks of

intervention by an independent statistician. The sample size adjustment will be made to ensure the appropriate power to determine the effect of UV exposure on vitamin D synthesis.

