# 3 Background/Rationale & Purpose

# 3.1 Background Information

Vitamin D deficiency has been a worldwide health problem for over a century, now affecting over 1 billion people on this planet. Although technology is drastically advancing, we still are unable to put an end to this health emergency.

Vitamin D can be introduced in the body in two ways, 1) via diet and 2) through the sun. Few foods naturally contain vitamin D (either  $D_2$  or  $D_3$ ) such as oily fish. For instance fresh wild salmon (3.5oz or

100g) has between 600-1000 IU of vitamin D3. Canned tuna (3.6oz or 102 g) has about 230 IU of vitamin D3. Sun-dried mushrooms and egg yolks are also viable sources of vitamin D. Sun-dried shiitake mushrooms have about 1600 IU of vitamin D2 whereas egg yolks have about 20 IU of vitamin D2 or vitamin D3. There are some fortified foods that also contain vitamin D; fortified milk and fortified orange juice each has about 100 IU/8 oz of vitamin D3. Some cereals, such as Quaker Oatmeal has as much as 40 IU vitamin D/cup. Margarine has about 60 IU of vitamin D/tablespoon. In a study that looked at the plasma levels of 25(OH)D3 amongst fish eaters and non-fish eaters (vegans and vegetarians), those who did not consume fish had lower levels of 25(OH)D3 in both the summer months (20%) and winter months (38%). Thus the consumption of fish in the diet is critical in maintaining vitamin D status throughout the year, especially during the winter months.

When assessing the optimal dietary intake of vitamin D, there might be some controversy as to which guideline to follow. The Institute of Medicine (IOM) issued guidelines to maintain adequate serum 25(OH)D levels above 20 ng/mL. The Endocrine Society's guidelines reflect the needs to treat and prevent vitamin D deficiency and maintain a 25(OH)D status above 30 ng/mL. One would have to consume a significant amount of fish and fortified food products to meet the above recommendations. Thus, it is critical that we incorporate sun exposure into our everyday lives, and/or take vitamin D supplements.

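### Conversion is labelled the MCID although the rise it needs runs from near 0 to 10 ng/mL or more, and the conversion model leaves that known distance unused, at a modest cost in precision

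*Combined protocol and SAP*

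**What the plan says.** Section 12.2 makes a change of class the clinically important unit: "Subjects converted from vitamin D deficient/insufficient to insufficient/sufficient is considered a minimum clinical important difference (MCID". Its parameter table counts a move from deficient to either higher class and a move from insufficient to sufficient alike. Neither text nor table sets a least rise in ng/mL.

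The planning rates are "We expect at least 70% of vitamin D deficient/insufficient subjects in the treatment group to convert to insufficient/ sufficient" and "we expect maximum 30% of subject convert to insufficient/sufficient in sham control". The sample size is set "With the desired power of 80% and significance level" 0.01, giving 35 per group. In the analysis, "Two-sided P < .05 will be considered significant" (Section 12). On the continuous scale, "We expect that the serum levels of 25(OH)D will increase more than 10 ng/ml (SD=5ng/ml) after 16 weeks".

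Eligibility requires 25(OH)D below 30 ng/mL (Section 7.1). The level of 20 appears only in Section 3.1, which cites one body's "guidelines to maintain adequate serum 25(OH)D levels above 20 ng/mL" beside another body's 30. The plan never states where deficient ends and insufficient begins in this trial.

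Conversion at 16 weeks is compared by Fisher's exact test and "logistic regression adjusting for skin types" (Section 12). Randomisation is stratified by age, sex, BMI and skin type (Section 5), not by baseline 25(OH)D. Section 12 also compares change in 25(OH)D (Mann-Whitney test, and linear regression adjusted for skin type) and fits a mixed model that adjusts for baseline and season. All of these have a continuous outcome.

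**The concern.** An MCID names a size of change; crossing a class limit does not. With limits at 20 and 30, a subject at 19.5 succeeds with a rise of 0.5 ng/mL, while a subject at 20.5 who rises by 9 reaches 29.5 and fails. Calling every conversion clinically important credits some rises no larger than ordinary variation and scores some large ones as failures.

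The distance to the next limit can be computed before the first exposure and goes far to decide who converts. A model without it treats that variation as unexplained. Section 3.2 says the trial must show its result with statistical significance, and about 35 evaluable subjects per arm are expected, so the lost precision is worth recovering. It has to be prespecified: a covariate added after unblinding would not be credible.

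**Working it through.** **1. The plan's own figure.** Inputs from Section 12.2: p1 = 0.7, p2 = 0.3, equal groups, z values 2.58 and 0.84.

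N = (2.58 × √0.5 + 0.84 × √0.42)² / 0.4² = (1.824 + 0.544)² / 0.16 = 35.07; the plan states 35. Unrounded z values give 36. Power at 35 per arm by the same approximation is 80.0% at alpha 0.01 and 93.5% at 0.05, so the stated power reproduces. Fisher's exact test has 74.6% and 88.2% at 35 per arm (80.5% and 94.1% at 40). That gap comes from the conservatism of the exact test and is a separate matter.

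**2. Rise needed to convert** for baseline b (limits 20 and 30, the former assumed): r = 20 − b if b < 20; r = 30 − b if 20 ≤ b < 30.

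| b (ng/mL) | 8 | 19.5 | 19.9 | 20 | 20.5 | 29.9 |
|---|---|---|---|---|---|---|
| r (ng/mL) | 12 | 0.5 | 0.1 | 10 | 9.5 | 0.1 |

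**3. How strongly r predicts conversion.** With a normally distributed change of mean m, P(convert) = Φ((m − r)/SD). At the plan's SD of 5:
- m = 0: 46% at r = 0.5, 42% at 1, 16% at 5, 2% at 10.
- m = 10: 50% at r = 10, 35% at r = 12.

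Averaged over the baseline shapes in step 4, 17-20% convert with no mean change at SD 5, and 11-12% at SD 3. About 18-22% of subjects start within 2 ng/mL of a limit. With arm means set to give 70% and 30%, and across a similar set of assumed baselines, 31-51% of sham converters rise by less than 5 ng/mL and 31-58% of UVB non-converters rise by 5 or more.

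**4. Power with and without r.** Simulation at 35 per arm with likelihood-ratio logistic tests and 1,500 trials per scenario (error about 1 point). Assumed baselines, all kept between 4 and 30: uniform 10-30; N(21, 3), from the case series in Section 12.2; N(22, 6); N(22.8, 13.9), from the pilot in Section 3.1. Mean changes were solved to give 30% and 70% (for the uniform baseline at SD 5: 1.94 and 8.06 ng/mL). Ranges are across baselines.

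| SD | alpha | without r | with r |
|---|---|---|---|
| 5 | 0.01 | 81.3-82.3% | 88.9-91.7% |
| 5 | 0.05 | 91.7-92.5% | 96.5-97.9% |
| 3 | 0.01 | 82.2-84.1% | 95.8-97.3% |
| 3 | 0.05 | 93.2-93.9% | 99.1-99.6% |

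These fits have no skin-type terms. With skin type in both models and further baseline shapes, the SD 5 ranges become about 81-84% against 87-92% at 0.01, and 92-95% against 96-98% at 0.05. At a smaller effect (56% against 30%, an assumption), power at 0.05 and SD 5 goes from 57-65% to 68-73%.

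**5. Two checks.** A linear baseline term in place of r adds only 0 to about 4 points, because r falls to zero at 20, jumps to 10 and falls to zero again at 30. At nominal 5%, the size is about 5-7% without r and 6-8% with it.

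**The case against.** The case on the other side is strong, and several inferences that a reader might draw from the working fail.

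- *The trial is underpowered.* Not supported. The 70% and 30% are marginal rates that already contain chance conversions; Section 12.2 allows the sham rate for season and other influences. The sample size reproduces.
- *The result is biased.* Not supported. Under randomisation, an imbalance in distance is ordinary sampling variation, which the test already reflects. Leaving out a prognostic covariate is not an error.
- *The plan ignores baseline and the size of the rise.* Not supported. The secondary analyses describe the rise, and the mixed model adjusts for baseline. They do not make the conversion analysis more precise or correct the MCID label.
- *Chance decides outcomes because the covariate is missing.* Not supported. Chance crossings near a limit come from a dichotomous endpoint and would remain after adjustment. The SD of 5 also mixes assay error, season and true differences in response.

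It is also true that at the analysis level of 0.05 the gain at the planned effect is only a few points, and that the 20 ng/mL limit is assumed. Another lower limit L would move the range, but the pattern would stay: nearly no rise needed just below L, and 30 − L needed at L.

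**Conclusion.** The point holds in a limited form. Conversion has no fixed size in ng/mL, so the MCID statement does not stand; this follows from the definition and needs no simulation. A strong predictor that the trial already collects is left out of both the conversion analyses and the stratification. The loss is relative to an adjusted analysis: at SD 5 and the planned effect, roughly 6 to 10 points of power at alpha 0.01 and a few points at 0.05, with more at SD 3 or at smaller effects. These sizes rest on limits of 20 and 30, a normally distributed change and the assumed baseline shapes.

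**What to change.** In Section 12:

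1. State the two cut-offs that define deficient, insufficient and sufficient.
2. Define the needed rise as the next cut-off minus the pre-exposure baseline value, and enter it as a linear covariate with treatment and skin type in the conversion logistic model. Name this the main conversion analysis, with Fisher's exact test as its unadjusted companion.
3. Say which sample is the baseline. Section 4.1.1 puts it just before the first exposure, a note in Section 6.2 puts blood draws after exposure, and the screening sample may come from another laboratory (Section 5).
4. State how a Week 1 value of 30 ng/mL or more is handled, since no higher class remains to enter; for example, use the screening value that qualified the subject.
5. Replace the MCID sentence with a statement that conversion is a category change of no fixed size, and report the mean 25(OH)D change in converters and non-converters by arm. Do not use 2.5 ng/mL as an importance threshold: Section 12.2 gives it only as an expected rise per four-week assessment.

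The cost is wording and one derived variable, fixed before unblinding. Endpoint, visits and sample size stay as they are. The downsides to disclose are one more parameter, an odds ratio that is conditional on the needed rise and so differs from the one adjusted for skin type alone, and a likelihood-ratio test that is slightly liberal at this sample size.

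### Forty per group absorbs 12.5% dropout, not the stated 15%: at 15% loss 34 per group remain, one short of the planned 35

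*Combined protocol and SAP*

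**What the plan says.** Section 12.2 sizes the trial on conversion of vitamin D status. For the treated group: "We expect at least 70% of vitamin D deficient/insufficient subjects in the treatment group to convert to insufficient/ sufficient". For sham: "we expect maximum 30% of subject convert to insufficient/sufficient in sham control". It continues: "With the desired power of 80% and significance level" "of 0.01, the sample size in each group is 35". It then plans 40 randomised per group and closes the argument with: "In our experience, the rate of screen failure and subject dropout is 10-15%. Then, we expect to have at least 35 subjects per each group".

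Section 12 describes the same calculation: "The protocol includes a sample size calculation, which allowed for a loss to follow-up of 15" (per cent). It sets the analysis threshold: "Two-sided P < .05 will be considered significant". It names Fisher's exact test for the endpoint, together with logistic regression adjusted for skin type.

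On recruitment, Section 12.2 expects at least 80% of the Boston-area population to be below 30 ng/mL, and so screens about 100 people to obtain 80. The Protocol Summary and Section 9 give the same count. Section 5 opens its recruitment paragraph differently, "A total of 80 adult subjects with 5 skin types groups (I, II, III, IV and V/VI) will be enrolled for vitamin D" (deficiency screening), and a few sentences later also gives approximately 100.

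**The concern.** Three numbers are meant to fit together: 40 randomised per group, a loss of up to 15%, and at least 35 left. They do not. The 35 matters because it carries the stated 80% power. It also triggers the blinded sample size re-assessment in Section 12.2, which waits until 35 per group have completed four weeks of intervention. If a full 15% were lost before that point, the trigger as written could not be met.

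The sentence offered in support also uses a single rate for two different things. Screen failure happens before randomisation and determines how many people must be screened. Dropout happens afterwards and is the only one of the two that reduces the 40. A merged rate cannot be applied to the 40 or checked against the screening numbers. Section 3.2 says the study was required by the FDA, so the evaluable number and its allowance are likely to be checked.

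**Working it through.** **Inputs.** Conversion 70% and 30%, alpha 0.01 two-sided (the formula uses z = 2.58), power 80%, 40 per group, screen failure and dropout 10–15% combined, at least 80% below 30 ng/mL, about 100 screened (all Section 12.2). Loss of 15%, analysis at two-sided 0.05, Fisher's exact test (Section 12).

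**1. The plan's 35 reproduces.** With p̄ = 0.5 and equal groups,

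n = {2.58 × √(0.5 × 0.5 × 2) + 0.84 × √(0.21 + 0.21)}² / 0.4² = (1.824 + 0.544)² / 0.16 = 35.07.

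Unrounded z values give 35.01. Strict rounding up would give 36, but 35 is a fair reading of the formula.

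**2. Loss from 40 per group.**

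| Dropout | Remaining of 40 | Randomised per group to keep 35 |
|---|---|---|
| 10% | 40 × 0.90 = 36 | 35/0.90 = 38.9, so 39 |
| 12.5% | 40 × 0.875 = 35 | 35/0.875 = 40 |
| 15% | 40 × 0.85 = 34 | 35/0.85 = 41.2, so 42 |

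The statement of at least 35 is true up to 12.5% loss and fails by one subject per group at 15%.

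**3. What one subject per group costs.** On the plan's own formula,

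power = Φ[(0.4√n − z × √0.5) / √0.42].

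At alpha 0.01 (z = 2.576):
- n = 35: (2.366 − 1.821)/0.648 = 0.841, power 80.0%.
- n = 34: (2.332 − 1.821)/0.648 = 0.788, power 78.5%.

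For Fisher's exact test, power is the sum, over all pairs of converter counts with p ≤ alpha, of the product of the two binomial probabilities (0.70 and 0.30).

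| n per group | Plan's formula, 0.01 | Fisher, 0.01 | Fisher, 0.05 |
|---|---|---|---|
| 34 | 78.5% | 71.6% | 87.6% |
| 35 | 80.0% | 74.6% | 88.2% |
| 40 | 86.3% | 80.5% | 94.1% |

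Going from 35 to 34 costs 1.5 points on the plan's formula at 0.01. With Fisher's test it costs 3.0 points at 0.01 and 0.6 points at 0.05.

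**4. The merged rate.** The plan's flow is 100 screened, 80 randomised, 70 evaluable. That is 20/100 = 20% lost at screening, 10/80 = 12.5% lost after randomisation and 30/100 = 30% overall. A combined 10–15% does not describe this flow. If the figure is meant as dropout only, step 2 applies.

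**5. The screening count.** At 80% below threshold, 100 screened give 80, while 80 screened would give 64. The 80 in Section 5 is therefore not the count on which the plan rests.

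**The case against.** The 15% has a plausible origin: 35 × 1.15 = 40.25, or about 40. That is the common shortcut of multiplying up instead of dividing by the retained fraction. It explains the number but does not make 34 equal 35.

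The 10–15% sentence follows the allocation of 40 per group, so it can be read as loss from the 40 after the 25(OH)D screen has been counted. That reading is fair, and it removes the clash with the 20% screening loss. It leaves the 34 against 35, and the words still name screen failure.

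The lower end of the range is comfortable. At 10% loss 36 remain, and the sponsor's earlier military study lost 10 of 98 (10.2%), which would leave about 36 of 40. Nor need every dropout leave the analysis: Section 12 specifies intention-to-treat, Section 9 requires a final blood sample on early exit, and Section 12.2 plans a blinded re-assessment. These points stand and limit the consequence. None of them reconciles the two statements.

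A reader might go further and infer that 100 screened cannot supply 80 because people will also fail other criteria. The documents do not support that. They say at least 80% and approximately 100, and Section 9 puts a telephone screen on medical history and eligibility before the visit at which 25(OH)D is drawn. Some later failures are possible, such as the baseline pregnancy test, but no rate is given for them. If 85% were below threshold and 5% failed otherwise, 100 would give 80.75; at 90% and 10%, 81; at 80% and 5%, 76. These rates are assumptions. The margin is thin at the 80% floor, but there is no contradiction and no basis for a larger screening target.

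**Conclusion.** The point holds for the attrition statement. The 15% allowance and the expectation of at least 35 per group cannot both be true with 40 randomised per group; the allowance actually delivered is 12.5%. The merged screen-failure and dropout rate is unclear wording that should be separated. The 80 in Section 5 is a slip that the same section corrects.

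The size is minor: one subject per group at the upper end of the stated range. The power figures assume 70% against 30% conversion, equal loss in both groups, and every dropout leaving the comparison, so 34 is the pessimistic count at 15% loss.

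A reader might infer that attrition leaves the trial underpowered. The figures do not support that. At the 0.05 threshold named for analysis, Fisher power at 34 per group is still 87.6%. At 0.01 it is below 80% already at 35 (74.6%), so most of that shortfall comes from pairing Fisher's test with a sample size from the normal approximation, not from the missing subject. The difference between alpha 0.01 for sizing and 0.05 for analysis is a separate matter and has a larger effect on power than 34 against 35.

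**What to change.** - **Section 12.2:** state screen failure and post-randomisation dropout as separate rates, and apply only dropout to the 40. Replace the closing sentence with wording such as: *40 per group allows 12.5% loss; at 15% loss 34 per group remain*, followed by the power at 34 for the test and alpha that will be used.
- **Section 12:** change the 15% allowance so that it agrees with Section 12.2.
- **Section 5:** as a minor consistency edit, change the screening count of 80 to approximately 100.

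The cost is wording in three sections and a slightly less favourable stated allowance. No additional randomised subjects and no larger screening target are requested. If the sponsor prefers to keep 15% as a true allowance for 35 evaluable, the arithmetic requires 42 per group (84 in total), but the small gain in power does not by itself call for that.
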